2 STUDY OBJECTIVES

2.1 Primary objective

To evaluate the efficacy of 3 dose levels of oral CR845 compared to placebo in reducing the intensity of itch in Chronic Kidney Disease (CKD) patients with moderate-to-severe pruritus.

2.2 Secondary objective (s)

- To evaluate the efficacy of 3 dose levels of oral CR845 compared to placebo in improving itch-related quality-of-life measures in CKD patients with moderate-to-severe pruritus
- To evaluate the safety of 3 dose levels of oral CR845 in CKD patients with moderate-to-severe pruritus.

2.3 Exploratory objective

Not Applicable.

Statistical Analysis Plan (SAP)

3 STUDY DESIGN

3.1 General study design

This is a multicenter, randomized, double-blind, placebo-controlled study to evaluate the safety and efficacy of 3 dose levels (0.25, 0.5, and 1 mg) of oral CR845 in moderate-to-severe CKD patients with moderate-to-severe pruritus.

Total study duration for a single patient: up to approximately 18 weeks

- Screening Period: 7 to 28 days prior to randomization (Day -28 to Day -8)
- Run-in Period: 1 week prior to randomization (Day -7 to Day -1)
- Treatment Period: 12 weeks
- Follow-up Visit: 7-10 days after the End-of-Treatment Visit or Early Termination Visit

Eligible patients will enter a 7-day Run-in period during the week prior to randomization when they will be required to complete at least four 24-hr Worst Itching Intensity NRS worksheets. If patients continue to meet all inclusion and no exclusion criteria at the end of the 7-day Run-in period and their mean baseline Worst Itching Intensity NRS score is ≥ 5 , they will be randomized in a 1:1:1:1 ratio to receive orally once daily either placebo or CR845 tablets at doses of 0.25, 0.5 or 1 mg. The mean baseline NRS score is defined as the average of the non-missing scores reported from the start of the 7-day Run-in period (eligible patients cannot have more than 3 missing daily scores during the run-in period). Randomization will be stratified according to the patient's renal disease status: moderate CKD non-dialysis; severe CKD non-dialysis; severe CKD on dialysis. The randomization of severe CKD patients on hemodialysis will be capped at approximately 20% of the total sample size.

[figure not shown]
The planned sample size is approximately 240 (60 per treatment group) male and female CKD patients with moderate-to-severe pruritus (mean baseline 24-hour Worst Itching Intensity numerical rating scale (NRS) score ≥ 5). The sample size may be increased up to 480 patients (120 per treatment group) based on the results of a planned interim analysis (IA) to be conducted when approximately 50-60% of the planned 240 patients have been randomized and have either completed the 12-week Treatment period or have discontinued study drug early.

Statistical Analysis Plan (SAP)

The study schematic is shown in Figure 1.

Figure-1 CR845-210301 Study Schematic

3.2 Randomization and blinding

Before the start of the study, a computer-generated randomization schedule will be prepared. Randomization will be performed using an interactive voice or web response system (IVRS/IWRS). Patients will be randomized in a 1:1:1:1 ratio to receive either placebo or CR845 tablets at doses of 0.25, 0.5, or 1 mg. Randomization will be stratified according to the patient's renal disease status: moderate CKD non-dialysis; severe CKD non-dialysis; severe CKD on dialysis (ie, 3 categories). The randomization of severe CKD patients on hemodialysis will be capped at approximately 20% of the total sample size (ie, 48 of 240 patients).

Patients, investigators, study staff, and the sponsor will be blinded to study drug assignment. For medically urgent or emergent situations that necessitate knowledge of study drug assignment for patient management, the blind may be broken via the IVRS/IWRS. Whenever possible, the medical monitor should be contacted prior to breaking the blind. The sponsor and medical monitor will receive a report whenever a patient blind is broken.

3.3 Study treatments and assessments

As described in [Section 3.1](#), randomized patients will take study drug once daily for 12 weeks and a total of 84 doses of study drug. Each dose should be taken at least 2 hours prior to or after a meal, around the same time of day (patient should not lie down for at least 1 hour after swallowing the tablet).

For severe CKD patients on hemodialysis, the same requirement for meal timing of study drug is required but the study drug must not be taken until after their dialysis procedure on days when they receive dialysis.

A detailed description of procedures and assessments to be conducted during this study is summarized in the scheduled of study assessments in [Table 1](#).

Statistical Analysis Plan (SAP)

Table 1: Schedule of Events

Study Procedures	Screening Period		Treatment Period							Follow-up ^j	
	Screening Period	Run-in Period							EOT or Early Termination		
			1	2	4	6	8	10	12		
Visit Days	-28 to -7	-7 to -1	1	14	28	42	56	70	84 (or following discontinuation at any time)	7 to 10 days after EOT/Early Termination	
			<———— ±2 days —————>								
Administrative procedures											
Informed consent	X										
Inclusion/exclusion criteria	X		X								
Medical history	X										
Review drug dosing instructions with patient			X								
Randomization			X								
Safety and efficacy evaluations											
Physical examination	X										
Height	X										
Weight (this is the prescription dry body weight for hemodialysis patients)	X										
12-lead electrocardiogram	X		X ^a						X		
Vital signs ^b	X		X ^a	X	X	X	X	X	X		
Hematology	X		X ^a		X				X		
Serum chemistry	X		X ^a		X				X		
Serum pregnancy (females of childbearing potential only)	X		X ^a						X		
Dispense study drug and drug diary ^c			X	X	X	X	X	X			

Statistical Analysis Plan

Protocol Number: CR845-210301

Version: Final V3.0,

Date: 18Oct2019

Page 11 of 57

Statistical Analysis Plan (SAP)

Study Procedures	Screening Period		Treatment Period							Follow-up ^j
	Screening Period	Run-in Period							EOT or Early Termination	
	Study Week		1	2	4	6	8	10	12	
Visit Days	-28 to -7	-7 to -1	1	14	28	42	56	70	84 (or following discontinuation at any time)	7 to 10 days after EOT/Early Termination
			<———— ±2 days —————>							
Patient training on PRO worksheets		X ^{d,e}	X ^e							
Worst Itching Intensity NRS (daily)		X	X ^f						X	
Skindex-10, 5-D Itch Scale, Patient Global Impression of Worst Itch Severity ^g			X ^a		X		X	X	X	
Patient Global Impression of Change									X	
Adverse event assessment			<—————>							
Prior medications		X								
Concomitant medications ^h			<—————>							

CKD = chronic kidney disease; EOT = end of treatment; NRS = numerical rating scale; PRO = patient-reported outcome

- a) To be collected/Performed prior to the first dose of study drug on Day 1.
- b) Vital signs, including body temperature, heart rate, and blood pressure, will be obtained while the patient is in a sitting or semi-recumbent position.
- c) Study drug will be dispensed to patients in bottles of 15 tablets following randomization on Day 1 and thereafter at each visit during the Treatment Period until the end of treatment/early termination visit. Patients may be contacted to verify or remind them to take their tablet daily per the protocol. Patients must record when they took the study drug in a drug diary every day during the Treatment Period.
- d) Training on Worst Itching Intensity NRS on the first day of the Run-in Period.
- e) Training on Skindex-10, 5-D Itch, and Patient Global Impression of Worst Itch Severity may be performed at any time during the Run-in Period or on Day 1 of the Treatment Period.
- f) Patients will be requested to complete the NRS worksheets at a similar time each day.
- g) Skindex-10, 5-D Itch, and Patient Global Impression of Worst Itch Severity are to be completed at the clinical site.
- h) Concomitant medications will be updated at each study visit following the first dose of study drug on Day 1.
- j) A phone follow-up will be conducted, unless otherwise necessary.

4 STUDY ENDPOINTS

4.1 Primary efficacy endpoint

The primary efficacy endpoint is defined as the change from baseline to week 12 of the Treatment period with respect to the weekly mean of the daily 24 hour Worst Itching Intensity NRS score.

4.2 Secondary efficacy endpoint(s)

The secondary efficacy endpoints of this study are:

- Change from baseline in itch-related quality of life at the end of week 12, as assessed by the total Skindex-10 scale score;
- Change from baseline in itch-related quality of life at the end of week 12, as assessed by the 5-D Itch Scale score;
- Proportion of patients achieving an improvement from baseline ≥ 3 points with respect to the weekly mean of the daily 24-hour Worst Itching Intensity NRS score at Week 12 of the Treatment period.

4.3 Additional efficacy endpoint(s)

The additional efficacy endpoints of this study are:

Itch-intensity Measures

- Proportion of patients who have an improvement from baseline at each week of the Treatment period and end of treatment with respect to the weekly mean of the 24-hour Worst Itching Intensity NRS scores ≥ 1 , ≥ 2 , ≥ 3 (excluding week 12) and ≥ 4 points.
- Proportion of “complete responders” with respect to Worst Itching Intensity score NRS at each week of the Treatment period and at end of treatment. A patient that has $\geq 80\%$ of the non-missing daily NRS scores in a week equal to 0 or 1 is considered a complete responder at that week.
- Change from baseline in the weekly mean of the 24-hour Worst Itching Intensity NRS score at each week of the Treatment period (Week 1 to Week 11) and at end of treatment.
- Proportion of patients who rate their itch condition as “Very much improved” or “Much improved” at Week 12/end of treatment, as measured by the Patient Global Impression of Change (PGIC).

Statistical Analysis Plan (SAP)

- Proportion of patients in each of the 5 categories of the Patient Global Impression of worst itch severity at baseline and at each scheduled weekly visit of the Treatment period and end of treatment.
In addition:
 - Proportion of patients who have a 1-point improvement or more from baseline
 - Proportion of patients who indicate a severity of 'None'.

Itch-related Quality-of-Life Measures

- Change from baseline in itch-related quality of life at each scheduled weekly visit of the Treatment period (excluding Week 12) and end of treatment, as assessed by the total score of the 5-D Itch Scale.
In addition, at each scheduled weekly visit of the Treatment period and end of treatment:
 - Proportion of patients who either rate the degree of itching intensity over the past 2 weeks as 'Not Present' or the direction of itching as 'Completely Resolved' from the 5-D Itch Scale.
 - Proportion of patients with itching present at each body part and the shift from baseline.
- Change from baseline in itch-related quality-of-life at each scheduled weekly visit (excluding Week 12) of the Treatment period and end of treatment, as assessed by the total score of the Skindex-10 Scale.
- Change from baseline in itch-related quality-of-life at each scheduled weekly visit of the Treatment period and end of treatment with respect to each of the 3 domains of the Skindex-10 Scale.
- Change from baseline in itch-related quality-of-life at each scheduled weekly visit (excluding Week 12) of the Treatment period and end of treatment with respect to each of the domains of 5-D Itch Scale.

4.4 Safety endpoint(s)

The safety assessments to evaluate the overall safety of CR845 will include,

- Adverse events
- Vital signs
- 12-lead Electrocardiograms (ECGs)
- Clinical laboratory evaluations
- Exposure to Study Drug and Compliance

Statistical Analysis Plan (SAP)

5 SAMPLE SIZE AND POWER

The minimum total sample size for this study is $N = 240$ patients (60 per treatment group) and the maximum is $N = 480$ (120 per treatment group). An unblinded interim analysis (IA) will be conducted when approximately 50-60% of the planned 240 patients have been randomized and have either completed the 12-week Treatment period or have discontinued study drug early. The primary goal of the IA is to identify dose(s) of oral CR845 that are both safe and efficacious. Doses that are found to be unsafe or poorly tolerated will be dropped from the study. No dose will be dropped for futility reasons. The details of sample size re-estimation based on conditional power are described in [section 8.9.1](#). A sample size of 60 patients per treatment group (the minimum sample size) will provide adequate power ($\geq 80\%$) for effect sizes ≥ 0.52 for a 5% type 1 error and a 2-sided T-test. Assuming a standard deviation of 2.6 for the primary efficacy variable, an effect size of 0.52 corresponds to a difference of approximately 1.4 point on a 0- to 10-point scale.

A sample size of 120 patients per treatment group (the maximum sample size) will provide adequate power ($\geq 80\%$) for effect sizes ≥ 0.40 for a 5% type 1 error and a 2-sided T-test. Assuming a standard deviation of 2.6 for the primary efficacy variable, an effect size of 0.40 corresponds to a difference of approximately 1 point on a 0- to 10-point scale. The power of a 2-sided hypothesis test with a 5% Type 1 error as a function of sample size and effect size is presented below.

Power as a Function of Effect Size (N = 120 Per Arm)^a

Effect Size	0.55	0.52	0.50	0.45	0.40	0.35
Power (N = 120)	98%	97%	97%	93%	86%	77%
Power (N = 60)	84%	80%	77%	68%	58%	47%

^a Power for a 2-sided T-test with equal variance and a 5% Type 1 error.

6 ANALYSIS POPULATIONS

6.1 Enrolled Population

The enrolled population is defined as the group of patients who sign the informed consent form (ICF).

6.2 Full Analysis Set (FAS)

The full analysis set is defined as all randomized patients who received at least 1 dose of study drug. Patients in the full analysis set will be analyzed according to their randomized treatment, regardless of the actual treatment received. The Full Analysis set will be used to analyze all efficacy endpoints.

6.3 Safety population (Safety)

The safety analysis population is defined as all randomized patients who received at least 1 dose of study drug. Patients in the safety analysis population will be analyzed according to their actual treatment. The Safety Population will be used to analyze all safety endpoints.

6.4 Per-Protocol population (PP)

The Per-Protocol Population is defined as the subset of patients in the full analysis set who do not have any major protocol deviations that could affect the efficacy analyses. An analysis of the primary and secondary efficacy variables for the per-protocol population may be performed if more than 20% of the patients in the full analysis set are excluded.

The per protocol population include patients who:

- Received $\geq 80\%$ and $\leq 120\%$ of the planned study drug doses
- Had a mean baseline Worst Itching Intensity NRS score ≥ 5.0
- Had a non-missing average 24-hour weekly Worst Itching NRS score available for at least 75% of study weeks (weeks with >3 missing daily values are missing)
- Did not have significant amounts of restricted and prohibited medications listed in protocol Section 6.4.7.2.
- Did not have major protocol violations that would impact efficacy outcomes.
- Satisfied all major inclusion and exclusion criteria on study entry and received treatment as planned.

Patients in the per-protocol population will be analyzed according to their actual treatment.

Statistical Analysis Plan (SAP)

6.5 Protocol deviations/violations and exclusions from analysis sets

All violations and exclusions of patients from analysis sets will be identified through programmatic checks, through medical reviews, and by clinical research associates during site monitoring. Protocol deviations will be classified as minor or major and whether they result in exclusion of the patient from the PP set, prior to the database lock.

7 STATISTICAL CONSIDERATIONS AND ANALYSIS

7.1 Derived Variables

The table below provides the list of derived variables for various duration derivations, drug compliance, baseline derivations and other important derivations applicable for this study.

Variables	Formula
Derivation of Duration	
Duration of treatment (days)	(Date of last dose of drug – date of first dose of study drug) + 1. (dates will be determined based on the patient daily dosing diary)
Duration of study (days)	(Date of study completion/discontinuation (for discontinued patients) – date of first dose) + 1
Study day	
 For dates before the date of first dose: Date of interest – date of first dose of study drug. For dates on or after the date of first dose: Date of interest – date of first dose of study drug + 1
Drug Compliance	
Compliance using accountability records	$[(\text{Sum of the total number of tablet dispensed across all visits} - \text{Sum of the total number of tablet returned across all visits}) / \text{Duration of treatment (days)}] * 100$
Compliance using daily dosing diary	$[(\text{Total number of tablet taken as per daily dosing diary}) / \text{Duration of study drug (days)}] * 100$
Baseline Derivations	
Baseline Worst Itching Intensity NRS score	The baseline score will be calculated as the average of the non-missing daily 24-hour Worst Itching Intensity NRS scores over the last 7 days prior to randomization; at least 4 completed Worst Itching Intensity NRS worksheets will be required prior to randomization.
Baseline (for other variables)	
 Time of assessment collected for the variable: baseline is defined as the last assessment prior to date/time of first dose of study drug whether scheduled or unscheduled. Time of assessment not collected for the variable: The baseline value is defined as the last observation prior to or on the date of the first dose of study drug whether scheduled or unscheduled
Change from baseline	Post baseline value – Baseline value

Statistical Analysis Plan (SAP)

Variables	Formula
Weekly Mean Worst Itching Intensity NRS score	
Weekly Mean Worst Itching Intensity NRS score	The weekly mean of the 24-hour Worst Itching Intensity NRS score will be defined as the sum of the daily Worst Itching Intensity NRS score reported during a specific week during the Treatment period (eg, Days 1 to 7, Days 8 to 14, Days 15 to 21, etc.) divided by the number of non-missing scores for that week. If there are <4 non-missing daily worst itching scores in a specific week, the corresponding weekly mean worst itching score will be set to missing.
Skindex-10	
Total Scores	Patients will be asked to fill in 1 of 7 circles numbered from 0 (labeled with the anchor phrase “never bothered”) to 6 (labeled as “always bothered”) for each of 10 questions. The total score is the sum of the numeric value of each answered question. For more details see Appendix B.
5-D Itch	
Total Score	Total 5-D Itch score = duration score (single item) + degree score (single item) + duration score (single item) + maximum disability (4 disability items) + category score based on sum of affected body parts. 5-D Itch scores can potentially range between 5 (no pruritus) and 25 (most severe pruritus). For more details see Appendix C

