7.2 Handling of missing data and outliers

7.2.1 Missing data analysis methods

For analyses relating to the Weekly Mean Worst Itching Intensity NRS score, Skindex-10 Total Score and 5-D Itch Total Score, missing data will be imputed using a multiple imputation (MI) approach. Details of imputation methods are described under [section 8.6.2](#).

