Statistical Analysis Plan (SAP)

dose group, the treatment group difference vs placebo will be estimated as the simple contrast in the treatment effect at Week 12 of the Treatment Period. The treatment difference between all doses combined and placebo will be estimated using a similar approach.

For week 12, the adjusted least square means (LS means) and standard error (SE) from the model will be presented for each treatment group. The LS means estimate for the difference, standard error, 95% CI, and p-value will also be presented. The primary analysis will be conducted using the Full Analysis Set. A summary table including descriptive statistics (n, mean, SD, median, minimum, maximum) for the observed value and the change from baseline by treatment group will also be provided for the NRS score.

An unstructured covariance matrix structure will be used to model the within patient errors. If there are convergence issues, other structures that require fewer parameters will be applied in the following order: 1) heterogeneous Toeplitz, 2) autoregressive, 3) compound symmetry until convergence is attained. The Kenward-Roger approximation will be used to estimate the denominator degrees of freedom.

For the MMRM analyses, the missing Weekly NRS score will be imputed using a Multiple Imputation (MI) approach, assuming that patients who discontinue study drug early would have similar Worst Itching Intensity NRS scores as other patients in their respective treatment arm that have complete data. The details of missing data imputations described as below.

- Intermittent missing weekly NRS scores will first be imputed using the Markov Chain Monte Carlo (MCMC) method implemented with the SAS MI procedure, which is appropriate for non-monotonic missing data. Additional terms for baseline NRS score and randomization stratification category (as dummy 0/1 variables) will be added. This will be performed within each treatment group separately.
- The monotone missing weekly NRS values will then be multiply imputed with the SAS MI procedure using the monotone regression method. The regression model will include terms for treatment group, baseline NRS score, and randomization stratification category; all previous non-missing post-baseline NRS scores will be included in the model. Should convergence issues occur due to small cell size for the categorical covariates at either stage, they will be removed from the model.

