- The change from baseline at Week 12 with respect to the weekly mean of the daily 24-hour Worst Itching Intensity will be analyzed for each imputed dataset using an MMRM model.
- One hundred imputations will be performed.

Statistical Analysis Plan (SAP)

- Results of the MMRM analysis on the multiply imputed data sets will be summarized by the SAS MIANALYZE procedure.

The details of MI SAS procedure described in [Appendix F](#).

In addition, sensitivity analyses of the primary efficacy endpoint will be conducted to evaluate the robustness of study results under different assumptions and imputation algorithms, as described below:

Sensitivity analysis 1 (No imputation; Missing at Random [MAR]):

In this sensitivity analysis, missing weekly worst itching scores will not be imputed. Assuming the data are MAR, the estimates of the treatment differences calculated from the MMRM model described above are unbiased. Details of analysis using SAS described under [Appendix G](#).

Sensitivity analysis 2 (Multiple Imputation; Missing Not at random (MNAR))

This sensitivity analysis is an implementation of a pattern mixture model that draws from different populations based on the reason for withdrawal.

- Intermittent missing NRS scores will first be imputed using the MCMC method with the SAS MI procedure, which is appropriate for non-monotonic missing data. This will be performed within each treatment group separately.
- For patients who discontinue study drug due to adverse events, data missing after discontinuation will be imputed using the distribution of the baseline value of all patients' weekly worst itching score with the same renal status assuming a trimmed normal (from 5 to 10).
- For patients who discontinue study drug due to reasons other than adverse event, monotone missing weekly NRS values will be multiply imputed with the SAS MI procedure using the monotone regression method applied to all patients with data available at the particular visit (including those withdrawing due to an adverse event). The regression model will include terms for treatment group, baseline NRS score, and randomization stratification category; all previous non-missing post-baseline NRS scores. Should convergence issues occur due to small cell size for the categorical covariates at either stage, they will be removed from the model.
- Results of the MMRM on the multiply imputed data sets will be summarized by the SAS MIANALYZE procedure.

Statistical Analysis Plan (SAP)

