8.6.3 Analysis of secondary efficacy endpoint(s)

The key secondary efficacy endpoints are:

- Change from baseline in itch-related quality of life at the end of Week 12, as assessed by the total Skindex-10 scale score;
- Change from baseline in itch-related quality of life at the end of Week 12, as assessed by the total 5-D Itch scale score;
- Proportion of patients achieving an improvement from baseline ≥ 3 points with respect to the weekly mean of the daily 24-hour Worst Itching Intensity NRS score at Week 12 of the Treatment period.

The Skindex-10 scale total score and the 5-D Itch total scale score will be analyzed using MMRM that will contain treatment, week, and treatment-by-week interaction as fixed effects; baseline score and renal disease status as covariates. Repeated measures will include values that reflect the Skindex-10 and 5-D total score at the end of weeks 4, 8, 10, and 12. The total score derivation for Skindex-10 and 5-D Itch scale detailed in [Appendix B](#) and [Appendix C](#) respectively.

The baseline value will be defined as the value of the Skindex-10 or 5-D Itch total score collected on Day 1 prior to randomization. Missing Skindex-10 Itch scale and 5-D Itch scale

Statistical Analysis Plan (SAP)

total scores will be imputed in a similar fashion as the primary endpoint for the MMRM analyses using the MI approach assuming data is missing at random. The mean treatment difference between each CR845 dose and placebo, and between all CR845 doses combined and placebo will be estimated as the simple contrast in the treatment effect at Treatment period week 12.

Descriptive statistics will be provided for the observed value and change from baseline at week 12 by treatment group for Skindex-10 scale and the 5-D Itch total scores. The adjusted LS means and SE from the model will be presented for each treatment group. The LS means estimate for the difference, standard error, 95% CI, and p-value will be presented. The analysis will be conducted using the Full Analysis Set.

An unstructured covariance matrix structure will be used to model the within patient errors. If there are convergence issues, other structures that require fewer parameters will be applied in the following order: 1) heterogeneous Toeplitz, 2) autoregressive, 3) compound symmetry until convergence is attained. The Kenward-Roger approximation will be used to estimate the denominator degrees of freedom.

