- The total Skindex-10 score is subdivided into 3 domain scores, which are sums of the scores of the following consideration of questions ([Appendix B](#)): disease domain (questions 1 to 3), mood/emotional distress domain (questions 4 to 6), and social functioning domain (questions 7 to 10). Change from baseline in itch-related quality of life at each of the post baseline weeks of the treatment period with respect to each of the 3 domains of the Skindex-10 Scale will be calculated. Treatment differences with respect to each domain will be evaluated using a model similar to the MMRM fitted for the analysis of the change from baseline in the total score of the Skindex-10 Scale.
- Change from baseline in itch-related quality of life at week 12 of the treatment period and at each of the remaining weeks of the treatment period with respect to each of the domains of 5-D Itch scale. Treatment differences with respect to each domain will be evaluated using a model similar to the MMRM fitted for the analysis of the change from baseline in the total score of the 5-D Itch Scale. The domain score derivation will be considered as detailed in the [Appendix C](#).

Listings will be provided for the variables used in the additional efficacy endpoints (which are not mentioned in the primary or secondary analysis).

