10. The effect of your itching making it hard to work or do what you enjoy							

Date Completed:
 D D M M M M Y Y Y Y

Time: :
 AM PM

SUBJECT INITIALS
First Middle Last

Patients will be asked to fill in 1 of 7 circles numbered from 0 (labeled with the anchor phrase “never bothered”) to 6 (labeled as “always bothered”) for each of the 10 questions. The total score is the sum of the numeric value of each answered question. The total score is subdivided into 3 domain scores, which are sums of the scores of the following questions: disease domain (questions 1 to 3), mood/emotional distress domain (questions 4 to 6), and social functioning domain (questions 7 to 10).

Statistical Analysis Plan (SAP)

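### The Skindex-10 total adds up answered items only, so a skipped item scores as 0 (never bothered), and the readable imputation text acts only on missing totals

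*SAP*

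**What the plan says.** SAP 7.1 defines the Skindex-10 total in one sentence: "The total score is the sum of the numeric value of each answered question". SAP Appendix B and protocol 6.5.1.2 give the same rule. There are ten items, each from 0 (never bothered) to 6 (always bothered), so a complete form totals 0 to 60. The three domains are plain sums as well: "The total score is subdivided into 3 domain scores, which are sums of the scores of the following questions". SAP 8.6.4 analyses them in the same way as the total: "Treatment differences with respect to each domain will be evaluated using a model similar to the MMRM fitted for the analysis".

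On missing data, SAP 7.2.1 states: "Skindex-10 Total Score and 5-D Itch Total Score, missing data will be imputed using a multiple imputation (MI) approach". It refers to 8.6.2 for details. SAP 8.6.3 names the unit to be imputed: "total scores will be imputed in a similar fashion as the primary endpoint for the MMRM analyses using the MI approach". The steps in 8.6.2 work on the derived weekly score, not on the daily scores behind it: "Intermittent missing weekly NRS scores will first be imputed using the Markov Chain Monte Carlo (MCMC) method". The code is placed in an appendix ("The details of MI SAS procedure described in"), and the SAS appendices are blacked out in the public copy.

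The same table in 7.1 treats the itch NRS differently. The weekly mean divides by the number of non-missing daily scores and is set to missing when fewer than 4 are available.

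**The concern.** On this scale 0 is a real answer, and the best one. A rule that drops unanswered items from a sum therefore turns a blank into full relief on that item. The resulting total is not missing, so imputation of missing totals would never reach it, and the form enters the repeated-measures model as fully observed.

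SAP Section 9 extends multiple imputation to the Skindex-10 so that missing data are not ignored. The item-level rule works against that aim.

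The total feeds the Week 12 contrasts, the pooled-dose comparison, the dose-trend test, the renal-status analyses and the interim summary. It is also reported descriptively by arm, where skips move the means directly even if the contrast barely changes.

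Blanks are foreseeable. Items 8 to 10 ask about other people, social contact, and work or enjoyment. The Skindex-10 form shows no not-applicable box, whereas the 5-D form has one for comparable activities. That some patients would leave such items blank is an inference; the documents do not say so.

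**Working it through.** No figure in the plan depends on this rule, so there is none to reproduce. The check is direct arithmetic.

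**Inputs from the documents:** ten items scored 0-6; total = sum of answered items.

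**Inputs assumed, because the documents give none:** skip rates, item means, the true treatment difference and the SD of change.

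**One form**

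With every item at v and k items skipped, the rule gives v × (10 − k) instead of 10v.

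- Unchanged patient, v = 4 at both visits, true change 0. Skipping 1, 2 or 3 items at Week 12 gives 36, 32 or 28, which are apparent improvements of 4, 8 or 12 points.
- Improved patient, items 4 at baseline and 2 at Week 12, true change 20 − 40 = −20. One skip at Week 12 gives 18 − 40 = −22.

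**Dose-placebo contrast, one-item skips at Week 12**

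Error in favour of drug = p_drug × v_drug − p_placebo × v_placebo, where p is the share of forms with a skip and v is the true value of the skipped item.

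(a) Equal skipping. If the skipped item carries an average share of a true difference D, then v_placebo − v_drug = D/10 and the error is −p × D/10, a fraction p/10 of D.

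| p | fraction of D | D = 5 | D = 20 |
|---|---|---|---|
| 5% | 0.05/10 = 0.5% | 0.025 points | 0.10 points |
| 10% | 0.10/10 = 1.0% | 0.05 points | 0.20 points |

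The effect is understated. If item values are also equal between arms, the error is 0.

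(b) Unequal skipping, 10% versus 5%, same item value in both arms:

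- item worth 3: 0.10 × 3 − 0.05 × 3 = 0.15 points
- item worth 4: 0.10 × 4 − 0.05 × 4 = 0.20 points

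For an assumed SD of change of 8 to 15, this is 0.15/15 = 0.010 SD to 0.20/8 = 0.025 SD, in favour of the arm that skips more.

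(c) Wider range. If the mean number of skipped items per form differs by 0.05 to 0.20 and item means are 3 to 5, the error runs from 0.05 × 3 = 0.15 to 0.20 × 5 = 1.0 points.

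**Baseline skips**

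SAP 8.6.3 fixes baseline before treatment assignment: "The baseline value will be defined as the value of the Skindex-10 or 5-D Itch total score collected on Day 1 prior to randomization". Baseline is also a model covariate, so skips there should add measurement error without biasing the contrast. A simulation checked this with 500,000 patients per arm; item means of 3.95 at baseline, then 2.05 on drug and 3.00 on placebo at Week 12; and SD of change 10.1. The true adjusted difference was −9.41.

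| Scenario | Shift at 5% | Shift at 10% |
|---|---|---|
| Skips at baseline only | +0.0002 | +0.0007 |
| Equal skips at Week 12 | +0.050 (0.54%) | +0.091 (0.97%) |

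Formula (a) predicts 0.047 and 0.094 for the second row, in agreement.

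**The case against.** The strongest case is that this is a minor clarification. On the scenarios in (a) and (b) the error is at most 0.025 SD or 1.0% of the effect. Every magnitude rests on assumed rates, and the fivefold gap between the 0.20 and 1.0 upper figures shows that the assumptions set the size. False benefit needs skipping, or the value of skipped items, to differ by arm. In a double-blind trial with identical tablets the documents give no reason to expect that. Forms are completed at the clinical site after training, under instructions in the Study Reference Manual, and monitors review the case report forms for completeness. Trial success and sample-size re-estimation do not use the Skindex-10. An item-level rule might also exist in the blacked-out appendices or in that manual. Finally, SAP 7.2.1 speaks of missing data in analyses of the total and does not expressly limit imputation to missing totals.

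Most of this stands as a limit on size. It does not remove the point. The scoring rule is written out in three places, and followed literally it gives a wrong value whenever the true answer to a skipped item is not 0. SAP 8.6.3 does name total scores as what is imputed. Site controls make blanks rarer but do not say how to score one. If a rule exists elsewhere, citing it in 7.1 would settle the matter.

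**Conclusion.** The concern holds. As written, a skipped Skindex-10 item counts as never bothered, and on the readable text a partly completed form goes into the analysis as observed. The certain part is the per-form error of 0 to 6 points of 60 for each skipped item. The effect on the dose-placebo contrast is likely small: 0.5-1.0% understatement with equal 5-10% skipping, or 0.15-0.20 points at 10% versus 5%. It reaches 1.0 point only if arms differ by 0.20 skipped items per form with item means of 5. All these rates are assumptions. Baseline skips do not materially bias the adjusted contrast. The primary endpoint and the decision on whether the study is positive are untouched. The correction should be made because the stated rule fails in a foreseeable case and costs almost nothing to change.

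**What to change.** Before final unblinding, replace the rule in SAP 7.1 and Appendix B with one item-level rule for baseline and all visits. Record it in Section 9, because protocol 6.5.1.2 carries the same definition. For example:

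- Prorate each domain (number of items × mean of answered items) when at least half of its items are answered; otherwise set it to missing.
- Take the total as the sum of the three domains, and set it to missing if any domain is missing, so that the planned imputation applies.
- State that a wholly blank form is missing, not 0.
- Report incomplete forms by arm and visit.
- Apply the same rule to any interim Skindex-10 totals that are reported again.

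To illustrate, take disease items 6, 6 and one skipped, with the seven other items at 2. The current rule gives 12 + 14 = 26. Domain proration gives 18 + 6 + 8 = 32. Prorating the total directly gives 10 × 26/9 = 28.9.

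The cost is a short SAP edit, a small change to the derivation code and one count table. The domain rule does send some nearly complete forms to imputation. With one blank it sends none. With two blanks it is C(3,2) + C(3,2) = 6 of C(10,2) = 45 patterns (13%). With three blanks it is 48 of C(10,3) = 120 (40%). Prorating the total directly once enough of the ten items are answered avoids this, but total and domains would then not always add up. The threshold is for the sponsor to choose, provided it is fixed in advance.
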